2.5 Correlative Studies Background

Provide background information on each planned correlative study including the biologic rationale and hypotheses as well as the relevant preclinical and clinical data.

3. PARTICIPANT SELECTION AND ENROLLMENT PROCEDURES

Refer to the Participant Eligibility Checklist in Appendix A.

3.1 Inclusion/ Exclusion Criteria We have decided not to duplicate the inclusion/exclusion criteria here, please refer to Appendix A.

3.2 Informed Consent Process

All participants must be provided a consent form describing the study with sufficient information for participants to make an informed decision regarding their participation. Participants must sign the IRB approved informed consent prior to participation in any study specific procedure. The participant must receive a copy of the signed and dated consent document. The original

signed copy of the consent document must be retained in the medical record or research file.

3.3 Randomization Procedures

Following enrollment, randomization will be carried out using pre-printed lists with block size of 4 through OnCore. Clinical research coordinators will complete the randomization process after consent completed.

3.4 Study Timeline

Primary Completion:

The study will reach primary completion 24 months from the time the study opens to accrual.

Study Completion:

The study will reach study completion 36 months from the time the study opens to accrual.

4. TREATMENT PLAN

We propose a randomized control trial with two arms; the experimental "HNC Virtual Coach" app group (Group A, n=88), and a paper logging control group (Group B, n=88). In clinical practice, many patients would not even complete paper log forms, therefore the act of logging alone may inflate adherence values. However, the ability to measure adherence across study groups required some level of logging to minimize the potential for recall bias. As a result, inclusion of the paper logging groups appeared to be the best compromise for comparing our experimental intervention with usual care. We hypothesize that those participants in Group A will complete a higher percentage of prescribed exercises than those in group B. Additionally, we hypothesize that those individuals in Group A will have more favorable swallowing outcomes as defined below.

Participants in the experimental arm (Group A) will receive a comprehensive swallowing rehabilitation app ("HNC Virtual Coach"). The paper group (Group B) will be given paper exercise logs to fill out. All patients will consult with a SLP prior to the initiation of radiation therapy. At that time, baseline evaluations of swallowing function (outlined below) will be performed. All participants will be educated regarding potential radiation-related side effects and trained in the same series of swallowing exercises by the SLP. In order to ensure fidelity of the target interventions, each SLP involved in this study will complete training with the site PI to ensure exercises and logging are being instructed according to the protocol. SLPs will ensure that the patient is able to return demonstrate each exercise during their visit.

Patients with elevated risk for developing dysphagia post-radiation will be the target of this intervention. This includes individuals with primary head and neck tumors in the oral cavity, oropharynx, nasopharynx, larynx, and hypopharynx requiring bilateral neck radiation. Patients with recurrent disease will be excluded from participation. Detailed inclusion and exclusion criteria can be found in Appendix A. Patients will be screened for eligibility, consented, enrolled, and randomized prior to the initiation of radiation therapy. Eligibility screening will be conducted through weekly screening of radiation oncology clinics, new patient referrals and tumor board patient lists. Those individuals identified as candidates for the study will be contacted by study personnel and educated regarding the trial. Interested participants will

be consented using an IRB approved consent form. Informed consent will explain to participants that they will receive an intervention to support their swallowing therapy during radiation. Following enrollment, randomization will be carried out using pre-printed lists with random block size. Subjects will meet with a member of the research team for a baseline visit that will review details on how to download and use the application or how to complete paper exercise logs. Written instructions regarding the app will be provided for patient reference at home. Participants will then be instructed to use the "HNC Virtual Coach" app in order to log daily exercises over the course of their treatment. All study subjects will proceed to routine clinical care, consisting of standard fractionated radiotherapy with or without concurrent chemotherapy (based on standard clinical indications). Participants in the experimental arm will be asked to use the "HNC Virtual Coach" program as an adjunct to standard care during treatment. The active study duration for each participant will begin on the first day of radiation. All participants will receive standard care with the SLP with planned clinical visits scheduled at the beginning of radiation, mid-way through radiation, and at the conclusion of radiation.

We have developed a demographic information instrument to allow us to properly describe our cohort and to examine possible effects of these factors on adherence and functional outcome measures. (Appendix L) Variables of interest include age, sex, ethnicity, disease stage, disease site, HPV status, education level, marital status, distance from home to treatment center, and insurance status. Additionally, participants will be asked to rate their comfort level with smartphone technology using a visual analogue scale (Appendix C). These will be completed at the time of study enrollment, prior to randomization.

Participants will be asked to complete and log their swallow exercises using either the Vibrent application or paper forms throughout the duration of radiation therapy. The Vibrent application will time stamp the date and time of data entry for secondary analysis to determine whether logging occurs on a daily basis or in batch. Paper logs will be collected by study personnel and entered into a central Redcap database. Each patient's program will ask the patient to complete 3 sets of ten repetitions of four different exercises, twice each day: Jaw stretches, Effortful Swallow, Mendelsohn Maneuver, and the Masako Maneuver. These maneuvers have all been well described and validated in the literature for patients undergoing treatment for head and neck cancer (Pauloski 2008).

Participants in the experimental arm (Group A) will receive a notification reminder to complete target exercises as well as a link to a video workout twice each day through the mobile application. Additional educational videos will also be made available through the "HNC Virtual Coach" program to support the patient with treatment-related toxicities that may impact exercise adherence during radiation (such as pain, fatigue, and xerostomia). All of these exercises and additional information are within the normal standard of care and are simply facilitated outside of the clinical setting by the "HNC Virtual Coach" program. When two sequential exercise sessions in a row are not completed, the application will push a survey to the participant to ascertain the reason why the sessions were not completed. Available options will include: 1) Didn't have time, 2) Pain, 3) Not feeling well/no energy, 4) Don't know how to do them, 5) Don't think they are necessary, 6) Issues with technology, and 7) Other. Based on participant responses, the study team will have the option to push information to the participant to address cited issues. During the baseline visit, the patients will be instructed that this mode of

communication is not intended to substitute the standard modes of communication with their provider, or obviate the need for scheduled follow-up visits. The communication portal rather serves as a real-time feedback component on the patients "out of clinic" course of treatment. Instructions will be given regarding any emergencies, with directions to not communicate via the system and to call 911 or go to the emergency room. In addition to these features, the app will also collect data regarding pain on a scale of 1-10 daily, where 1=no pain and 10=severe pain. This will allow investigators to monitor pain as a variable that may impact adherence. Additionally, in order to evaluate the relative role of oral intake during treatment, participants will be asked to rate their oral intake for nutrition/hydration as "all", "some", or "none" on a daily basis.

Participants in the paper control group (Group B) will be asked to log exercises on provided logging sheets (Appendix D). Both groups will be asked to rate their pain on a scale of 1-10 daily when they log their exercises either on the control app or on their paper logging sheets. We acknowledge that there are limitations to relying on patient logging as a measure of adherence. Unfortunately, there is no gold standard for measuring exercise adherence. A number of patient reported surveys have been reported in the literature; however these have been shown to have limited reliability and validity (McLean 2017). In the absence of validated, reliable measures of adherence, patient logging remains the mainstay for measuring adherence in the majority of the exercise literature. The reliance on patient logging across treatment arms will minimize the risk for reporting bias in this study.

Aim 1: To evaluate the impact of the "HNC Virtual Coach" mobile application on patient adherence to a prescribed swallowing therapy protocol.

Primary outcome variable: Overall adherence to prescribed exercise protocol measured as percentage of prescribed exercises completed over a seven-week period. (i.e. if participants are asked to complete 6 sets of 10 reps of each exercise daily for 7 weeks, maximum potential would be 420 sets).

Aim 2: To evaluate the impact of the "HNC Virtual Coach" program on the prevalence, characteristics, and severity of dysphagia in patients undergoing radiation therapy for head and neck cancer.

Secondary outcome variables:

Patient reported:

MD Anderson Dysphagia Inventory (MDADI) (Appendix E)

Clinician reported:

Functional Oral Intake Score (FOIS) (Appendix F)

Performance Status Scale – Head and neck (PSS HN) (Appendix G)

Functional measures obtained during videofluoroscopic swallowing studies (VFSS):

Penetration Aspiration Scale (PAS) (Appendix H)

Individual item and composite scores of the Modified Barium Swallow Impairment Profile (MBS-ImP) (Appendix I)

Dynamic Imaging Grade of Swallowing Toxicity (DIGEST) severity scores (Appendix J) Maximal interincisor distance

See study calendar for when these outcome measures will be collected

Modified barium swallow procedure: All MBS studies will follow a standard protocol. Additional boluses or strategies may be employed by the treating clinician only after completion of the study trials outlined below. Examinations will be conducted using a minimum of 30 frames per second and recorded for review purposes. Studies will be saved in AVI or MPEG format. Patients will be evaluated while seated in lateral and frontal views with views to include the soft palate superiorly, the cricopharyngeus inferiorly, the lips anteriorly, and the cervical spine posteriorly. A penny will be taped to the participant's chin during the evaluation to provide calibration for measurements performed following the MBS. Varibar contrast will be used in trials as outlined below:

Lateral view: 5cc Varibar thin liquid X2

10cc Varibar thin liquid X1 20cc Varibar thin liquid X1

Ungraded cup sip Varibar thin liquid X2

5cc Varibar pudding X2

½ graham cracker coated with 3ml Varibar pudding X1

Frontal view: 20cc Varibar thin liquid bolus X1

MBS videos from all sites may be stored in Stanford Medicine Box until the study's completion. The modified barium swallow videos will then be reviewed by a Stanford MBS-ImP trained SLP blinded to treatment group.

The MD Anderson Dysphagia Inventory (MDADI) was selected to capture and quantify the patient perception of swallowing dysfunction. It is a 20-item patient reported survey that measures the impact of dysphagia on patients with HNC. Each item is rated on a scale of 1-5 with lower numbers indicating poorer function. Mean subscale scores are multiplied by 20 to provide a final score between 20-100. This scale has been validated as a reliable tool to measure the impact of dysphagia on head and neck cancer patients (Chen 2001).

In order to describe patient diet levels, the Functional Oral Intake Scale was selected. The FOIS is a 7-point ordinal scale used to describe oral intake where lower scores reflect more limited oral intake and higher scores reflect more normal diet levels. Originally validated in patients with dysphagia following stroke, the FOIS was found to have very good inter-rater reliability and validity (Crary 2005). It has been used extensively in studies of dysphagia in the head and neck cancer population.

The Performance Status Scale – Head and Neck (PSS-HN) was chosen to provide additional detail regarding diet and eating restrictions. This measure has been validated and shown to have good correlation with other measures of function in this population (List 1990).

In order to measure physiologic swallow function during MBS studies, three assessment

tools were chosen. The Penetration Aspiration Scale is an 8-point interval scale used to describe degree of bolus entry into the laryngeal vestibule and patient response to this material. Lower scores reflect more normal function. It has been shown to have favorable intra- and inter- judge reliability (Rosenbek 1996).

The Modified Barium Swallow Impairment Profile is a tool designed to quantify degree of impairment on 13 individual physiologic components visualized during a modified barium swallow where higher numbers reflect greater dysfunction. This tool correlates significantly with other measures of swallowing including penetration aspiration scores, diet scores, and quality of life (Martin-Harris 2008).

The Dynamic Imaging Grade of Swallowing Toxicity was established to rate the safety and efficiency of the pharyngeal swallow during modified barium swallow studies using the National Cancer Institute's Common Terminology Criteria for Adverse Events (CTCAE) framework. The scale has been shown to correlate with the MBSImp composite score, MDADI, and oral intake levels (Hutcheson 2017).

These measures, in combination, provide a comprehensive evaluation of swallowing physiology, its functional impact, and patient perception.

4.1 Criteria for Removal from Study

Treatment failure is not a study endpoint. Study subjects will be removed when requested by study subjects. Cessation of the research procedure will not affect the routine clinical care a study subject receives as the study subject will still be receiving standard of care through their regularly scheduled clinic appointments. The use of the VibrentTM mobile application will only serve as an adjunct to this standard of care.

4.2 Alternatives

The alternative to participation in this trial is standard clinical care.

5. INVESTIGATIONAL AGENT/DEVICE/PROCEDURE INFORMATION

5.1 Investigational Agent/Device/Procedure

The "HNC Virtual Coach" program has been developed in conjunction with Vibrent Health (www.vibrenthealth.com), a cloud-based precision health platform for individual and population health. The Vibrent team has partnered with stakeholders across the healthcare ecosystem to advance disease prevention and treatment based on real-world evidence and scientific rigor. Vibrent has experience with leading edge technologies for both commercial contracts and academic grant projects including adaptive algorithms, wireless wearables and medical devices, passive sensing, predictive modeling, machine learning, adaptive tailored messaging, dynamic automated care planning, big health data system integration, genomics, and more. Vibrent was recently chosen by the National Institutes of Health (NIH) to provide the technology backbone for its historic Precision Medicine Initiative (www.joinallofus.org), engaging millions of Americans over the next ten years. This groundbreaking effort aims to engage more than one million participants to understand how genomics, lifestyle, behavioral, and environmental factors impact an individual's health. For the purpose of the current investigation, Vibrent Health will partner with head and neck cancer teams at a number of National Cancer Institute designated

Comprehensive Cancer Centers to optimize and evaluate a precision health platform to facilitate patient adherence to swallowing exercises and optimize functional swallowing outcomes.

For clinicaltrials.gov and Stanford Clinical Trials Directory compliance

Intervention Description

Participants in the experimental arm (Group A) will receive a notification reminder to complete target exercises as well as a link to a video workout twice each day through the mobile application. Additional educational videos will also be made available through the "HNC Virtual Coach" program to support the patient with treatment-related toxicities that may impact exercise adherence during radiation (such as pain, fatigue, and xerostomia). All of these exercises and additional information are within the normal standard of care and are simply facilitated outside of the clinical setting by the "HNC Virtual Coach" program. When two sequential exercise sessions in a row are not completed, the application will push a survey to the participant to ascertain the reason why the sessions were not completed. Available options will include: 1) Didn't have time, 2) Pain, 3) Not feeling well/no energy, 4) Don't know how to do them, 5) Don't think they are necessary, 6) Issues with technology, and 7) Other. Based on participant responses, the study team will have the option to push information to the participant to address cited issues. During the baseline visit, the patients will be instructed that this mode of communication is not intended to substitute the standard modes of communication with their provider, or obviate the need for scheduled follow-up visits. The communication portal rather serves as a real-time feedback component on the patients "out of clinic" course of treatment. Arms/Groups if arms or groups have been specified for the protocol, all arms must be described and have at least one intervention (unless arm type is "No Intervention") and each intervention must be assigned to at least one arm.

5.2 Availability

The mobile application will be provided by Vibrent Health.

5.3 Agent Ordering

The application will be downloaded from standard app stores with the assistance of the research coordinator.

6. ADVERSE EVENTS AND REPORTING PROCEDURES

6.1 Potential Adverse Events

No medical risks are expected to result from the use/implementation of the VibrentTM mobile application. The risk associated for all participants will not be greater than that of routine care for head and neck cancer patients receiving radiation therapy. No direct risk is anticipated for completion of questionnaires or use of mobile applications as patients already have familiarity with these devices throughout their daily lives.

6.2 Adverse Event Reporting

Since this is a low-risk study with no anticipated adverse events (AE) related to the intervention, we will not be collecting any AEs or SAEs.

7. STUDY CALENDAR

Schedules shown in the Study Calendar below are provided as an example and should be modified as appropriate.

	Pre- Study ¹	Wk 1	Wk 2	Wk 3	Wk 4 ²	Wk 5	Wk 6	Wk 7 ³	Wk 19 ⁴	1 Year ⁵
Optimize mobile application ⁷	X^7									
Paper Logs ¹²		X	X	X	X	X	X	X		
Informed consent	X									
Demographic Survey (Appendix L) ⁹	X									
Medical history ¹⁰	X									
Technology comfort scale (Appendix C) ⁸	X									
MD Anderson Dysphagia Inventory (Appendix E)	X								X	X
INFO 25 (Appendix K)	X								X	
Functional oral intake score (Appendix F)	X				X			X	X	X
Performance status scale H&N (Appendix G)	X				X			X	X	X
Weight	X				X			X	X	X
Maximal inter-incisor distance (mm) ¹³	X				X			X	X	X
Modified barium swallow ¹¹	X^6								X	X

Footnote:

- 1. Procedures to be completed any time prior to start of radiation treatment. If SOC procedures are completed prior to consent, they can be included, and do not need to be repeated.
- 2. Procedures to be completed during Week 4 of radiation treatment (+/- 2 days).
- 3. Procedures to be completed during final week of radiation treatment (+/- 2 days).

- 4. Procedures to be completed 3 months after end of radiation, ideally within (+/- 2 weeks). However, if the procedures cannot be completed during that window (+/-) 1 month is acceptable.
- 5. Procedures to be completed 1 year after end of radiation (+/- 1 month).
- 6. Pre-study MBSS should occur prior to start of radiation treatment, but can also occur within 2 days after start of radiation.
- 7. For patients randomized in the app arm of the study.
- 8. Part of the technology survey questions (the first 2 questions) are in the "pre-screening survey." When the patient is completing the technology survey, the first 2 questions can be left blank if the participant has already answered them in the pre-screening survey (Appendix M).
- 9. In addition to Appendix L, the following demographic information will be collected from source documentation: date of birth, age at enrollment, miles from residence to treatment center
- 10. Medical History: tumor site, TNM staging (8th edition), AJCC stage, HPV status, Primary treatment, Prescribed radiation dose (Gy), and Chemotherapy/Systemic Treatment
- 11. Modified Barium Swallow Study metrics (Appendix I) completed along with Penetration Aspiration Scale (Appendix H) and DIGEST scores (Appendix J)
- 12. For patients randomized to paper log arm of the study.
- 13. Provide patients with standard scale to measure MIO during video visits (via mail or during inperson visit)

8. MEASUREMENTS

For clinicaltrials.gov and Stanford Clinical Trials Directory compliance Primary Outcome Measure Definition: Overall adherence to prescribed exercise protocol measured as percentage of prescribed exercises completed over a seven-week period. (i.e. if participants are asked to complete 6 sets of 10 reps of each exercise daily for 7 weeks, maximum potential would be 420 reps).

* Title: Exercise adherence

* Time Frame: At the end of the 7 week treatment period

* Safety Issue: No

8.1 Primary Outcome Measure

Adherence to prescribed exercise protocol

(a) 8. 1.2 Measurement Definition

Overall adherence to prescribed exercise protocol measured as percentage of prescribed exercises completed over a seven-week period. (i.e. if participants are asked to complete 6 sets of 10 reps of each exercise daily for seven weeks, maximum potential would be 420 reps).

(b) 8.1.3 Measurement Methods

Participants will be asked to complete and log their swallow exercises using the either the Vibrent application or paper forms throughout the duration of radiation therapy and for 1 month after the completion of therapy. The Vibrent application will time stamp the date and time of data entry for secondary analysis to determine whether logging occurs on a daily basis or in batch. Paper logs will be collected by study personnel weekly and entered into a central Redcap database.

(c) 8.1.4 Measurement Time Points

Adherence measures will be obtained at the conclusion of the 7-week treatment period.

8.2a Secondary Outcome measures (These measures, in combination, provide a comprehensive evaluation of swallowing physiology, its functional impact, and patient perception.)

Patient reported:

MD Anderson Dysphagia Inventory (MDADI)

(d) 8.2a.2 Measurement Definition

The MD Anderson Dysphagia Inventory (MDADI) was selected to capture and quantify the patient perception of swallowing dysfunction. It is a 20-item patient reported survey that

measures the impact of dysphagia on patients with HNC. Each item is scored on a 5 point scale with 1=lower function and 5=higher function. Possible scores range from 20-100 with higher scores indicating more normal swallowing function. Mean scores will be assessed for each treatment group at the time of each assessment. Standard deviation and 95% CI will be reported.

(e) 8.2a.3 Measurement Methods

MDADI: Each item is rated on a scale of 1-5 with lower numbers indicating poorer function. Mean subscale scores are multiplied by 20 to provide a final score between 20-100. All participants will complete on paper forms.

(f) 8.2a.4 Measurement Time Points

Please see study schedule for the measurement time points.

8.2b Secondary Outcome measure

Functional Oral Intake Score (FOIS)

(g) 8.2b.2 Measurement Definition

In order to describe patient diet levels, the Functional Oral Intake Scale was selected. The FOIS is a 7-point ordinal scale used to describe oral intake where lower scores reflect more limited oral intake and higher scores reflect more normal diet levels. The mean group FOIS score will be reported as well as standard deviation and 95% CI at each assessment (see study calendar).

(h) 8.2b.3 Measurement Methods

FOIS score will be given by the treating clinician based on patient reported diet level.

(i) 8.2b.4 Measurement Time Points

Please see study schedule for the measurement time points.

8.2c Secondary Outcome measure

Performance Status Scale – Head and neck (PSS HN)

(j) 8.2c.2 Measurement Definition

The Performance Status Scale – Head and Neck (PSS-HN) was chosen to provide additional detail regarding diet and eating restrictions. The three items which will be administered include "eating in public", "understandability of speech", and "normalcy of diet". Each item ranges from 0-100 with higher numbers reflecting more normal function. The mean group score will be reported as well as standard deviation and 95% CI at each assessment (see study calendar).

(k) 8.2c.3 Measurement Methods

PSS-HN will be completed by the treating clinician based on patient reports.

(1) 8.2c.4 Measurement Time Points

Please see study schedule for the measurement time points.

8.2d Secondary Outcome measure

Functional measures obtained during videofluoroscopic swallowing studies (VFSS)
Penetration Aspiration Scale (PAS)

(m)8.2d.2 Measurement Definition

In order to measure physiologic swallow function during MBS studies, three assessment tools were chosen. The Penetration Aspiration Scale is an 8-point interval scale used to describe degree of bolus entry into the laryngeal vestibule and patient response to this material. Higher numbers reflect more severe laryngeal penetration/aspiration. The mean group score for most severe PAS will be reported as well as standard deviation and 95% CI at each assessment (see study calendar).

(n) 8.2d.3 Measurement Methods

MBS ratings (PAS, MBS-Imp, DIGEST) will be rated by clinicians blinded to group assignment based on review of videotaped assessments.

8.2d.4 Measurement Time Points

Please see study schedule for the measurement time points.

8.2e Secondary Outcome measure

Functional measures obtained during videofluoroscopic swallowing studies (VFSS) Individual item and composite scores of the Modified Barium Swallow Impairment Profile (MBS-ImP)

(o) 8.2e.2 Measurement Definition

The Modified Barium Swallow Impairment Profile is a tool designed to quantify degree of impairment on 13 individual physiologic components visualized during a modified barium swallow where higher numbers reflect greater dysfunction. The mean group score for the composite oral component and pharyngeal component will be reported as well as standard deviation and 95% CI at each assessment (see study calendar).

(p) 8.2e.3 Measurement Methods

MBS ratings (PAS, MBS-Imp, DIGEST) will be rated by clinicians blinded to group assignment based on review of videotaped assessments.

(q) 8.2e.4 Measurement Time Points

Please see study schedule for the measurement time points.

8.2f Secondary Outcome measure

Functional measures obtained during videofluoroscopic swallowing studies (VFSS)

Dynamic Imaging Grade of Swallowing Toxicity (DIGEST) severity scores

(r) 8.2f.2 Measurement Definition

The Dynamic Imaging Grade of Swallowing Toxicity was established to rate the safety and efficiency of the pharyngeal swallow during modified barium swallow studies using the National Cancer Institute's Common Terminology Criteria for Adverse Events (CTCAE) framework. This scale provides a safety impairment score, an efficiency impairment score, and an overall score. Lower numbers on this scale are indicative of more normal function. The mean group impairment scores will be reported as well as standard deviation and 95% CI at each assessment (see study calendar).

(s) 8.2f.3 Measurement Methods

MBS ratings (PAS, MBS-Imp, DIGEST) will be rated by clinicians blinded to group assignment based on review of videotaped assessments.

(t) 8.2f.4 Measurement Time Points

Please see study schedule for the measurement time points.

8.2g Secondary Outcome measure

Maximal interincisal opening

(u) 8.2g.2 Measurement Definition

Maximal interincisor distance will be reported in mm as the space between the bottom of the upper incisor and the top of the lower incisor. In patients missing dentition, 10mm will be deducted from this value for each missing incisor to represent the average incisal height.

(v) 8.2g.3 Measurement Methods

Standard mm measuring tools will be used.

(w) 8.2g.4 Measurement Time Points

Please see study schedule for the measurement time points.

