Appendix D: Paper logging form

Exercise logging form: Please indicate the number of sets of exercises prescribed you completed and denote your level of pain after completing the sets of exercises with 1 being no pain, and 10 extreme:

	Day 1	Day 2	Day 3	Day 4	Day 5	Day 6	Day 7
Date							
AM							
PM							
Pain Level (1- 10)							

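### The maximum of 420 in the primary endpoint definition does not follow from the exercise schedule beside it, and its unit is sets in one place and reps in two

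*Combined protocol and SAP*

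**What the plan says.** All places are in the combined protocol and SAP.

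- Section 4 (Treatment Plan) sets the programme: each patient is asked to "complete 3 sets of ten repetitions of four different exercises, twice each day". The exercises are jaw stretches, the effortful swallow, the Mendelsohn maneuver and the Masako maneuver.
- Section 4, under Aim 1, defines the primary outcome as a percentage of the prescribed exercise and illustrates the maximum: "6 sets of 10 reps of each exercise daily for 7 weeks, maximum potential would be 420 sets".
- Section 8 (Measurements), lead text, repeats the definition with another unit: "6 sets of 10 reps of each exercise daily for 7 weeks, maximum potential would be 420 reps".
- Section 8.1.2 has the unit of section 8: "6 sets of 10 reps of each exercise daily for seven weeks, maximum potential would be 420 reps".
- Appendix D, the paper log, has columns for Day 1 to Day 7 and one AM and one PM cell per day. Its instruction is "Please indicate the number of sets of exercises prescribed you completed".
- Sections 10.1 and 10.4 name logistic regression for the primary endpoint and a linear mixed model for weekly adherence. Neither gives a maximum or an adherence cut-off.

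**The concern.** A percentage needs a denominator, and 420 is the only numerical maximum given for the sole primary endpoint. It stands inside the definition in all three places, and the statistical sections do not correct it. If a programmer took it at face value, the adherence percentages would be wrong. The two units cannot both hold either: at ten reps per set, 420 sets is 4,200 reps.

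**Working it through.** **Inputs.** Sets per session, reps per set, number of exercises and sessions per day come from section 4: 3, 10, 4 and 2. The duration is seven weeks (sections 4, 8 and 8.1.2). The programme is daily, and Appendix D has seven day columns per sheet, so there are 7 x 7 = 49 days.

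**Step 1: try to reproduce 420.** The schedule gives 3 x 2 = 6 sets of each exercise per day, which agrees with all three definitions. From there 420 is not reached. It appears only if an input is changed, for example:

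- 6 x 10 x 7 = 420, which is the reps of one exercise for one week;
- 3 x 4 x 5 x 7 = 420, which is the sets of all four exercises with one session a day on five days a week;
- 6 x 2 x 5 x 7 = 420, which is the sets of two exercises on five days a week.

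The documents do not say where 420 came from, and each of these contradicts the stated schedule.

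**Step 2: multiply out the stated schedule.**

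- Sets per exercise: 6 x 49 = 294.
- Reps per exercise: 294 x 10 = 2,940.
- Sets over four exercises: 294 x 4 = 1,176 (directly from section 4: 3 x 4 x 2 x 49 = 1,176).
- Reps over four exercises: 2,940 x 4 = 11,760.

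A weekdays-only reading (5 x 7 = 35 days), which the text does not support, gives 210 or 840 sets and 2,100 or 8,400 reps. None of these is 420.

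**Step 3: score a fully adherent patient against 420.**

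| What is counted | True maximum | Score with 420 as denominator |
|---|---|---|
| Sets, per exercise | 294 | 294/420 = 70% |
| Sets, all four | 1,176 | 1,176/420 = 280% |
| Reps, per exercise | 2,940 | 2,940/420 = 700% |
| Reps, all four | 11,760 | 11,760/420 = 2,800% |

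Three of the four exceed 100% and would probably be noticed. The 70% case would not announce itself.

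**Step 4: consequences of the 70% case,** with the planning values of section 12.6 (33% in arm B, a 15-point difference, SD 32) and the same wrong denominator in both arms.

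- Means: 33% is reported as 33 x 0.70 = 23.1%, and 48% as 48 x 0.70 = 33.6%. The difference is 10.5 points instead of 15.
- Standardised difference: 15/32 = 0.469. After scaling, the SD is 32 x 0.70 = 22.4, and 10.5/22.4 = 0.469. A comparison of means keeps it.
- A fixed cut-off c on the scored percentage would require true adherence of c/0.70. Fewer patients could qualify, and a cut-off above 70% could not be met at all.

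**Step 5: sample size.** Section 12.6 uses the difference, the SD and the dropout allowance. 420 does not enter.

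**The case against.** The best defence is that 420 sits in an illustrative parenthesis. The worded definition is the same in all three places, and section 4 gives the full prescription, so an analyst can derive the denominator without the figure. Nothing in the analysis or sample size sections uses it. That is fair and limits the weight of the point. It does not remove it: the parenthesis takes the trial's own prescription as its inputs, and it is the only place where the maximum is put into a number.

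It can also be said that the printed numerals 6, 10 and 7 do multiply to 420. They do, and a dropped factor of seven (days per week) is a plausible origin that would suit the unit reps. It is unproven, and the result would be one exercise's maximum for one week, not for seven.

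A reader might go further and infer that the arms will be scored on different scales. Appendix D has no row per exercise, so a complete session could be entered as 3 (per exercise) or 3 x 4 = 12 (summed), a factor of 4. For the app the documents state no stored unit; the wording "When two sequential exercise sessions in a row are not completed" describes a survey trigger, not the log. Section 4 also rests comparability on logging in both arms: "The reliance on patient logging across treatment arms will minimize the risk for reporting bias in this study". But a bias would need one arm counted per exercise, the other summed, and a common denominator for both. No passage says so. Appendix D does state a unit (sets), the therapists are trained "to ensure exercises and logging are being instructed according to the protocol", app users receive written instructions, and the app specification is not among these documents. What remains is a missing detail, not a demonstrated bias.

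**Conclusion.** The point holds as an error in the text of the primary endpoint definition. 420 is wrong in either unit, and the unit conflicts between section 4 (sets) and sections 8 and 8.1.2 (reps). The stated schedule gives 294 sets or 2,940 reps per exercise, and 1,176 sets or 11,760 reps in all. This rests only on daily meaning seven days a week and on the prescription in section 4.

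Harm arises only if 420 is actually used as the denominator, which the documents do not show. Two opposite inferences should be avoided. One is that the sample size is affected; it is not. The other is that a uniform 70% scaling is harmless. That is true of the standardised difference in a comparison of means, such as the weekly mixed model. It is not true of the reported percentages, and it need not be true of the primary analysis: if the logistic regression uses a fixed adherence cut-off, the set of patients counted as adherent would change. No cut-off is stated, so the size of that effect cannot be given.

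A reader might also connect this with section 8.1.3, which has patients log for one month after therapy, while section 4 has logging during radiation only and the study calendar marks paper logs in weeks 1 to 7. That is a separate inconsistency. The endpoint is confined to seven weeks, so its denominator is unaffected.

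**What to change.** - Reconcile section 4 (Aim 1), section 8 and section 8.1.2 with the prescription in section 4, and replace 420 in each with the product of that prescription in one unit: 294 sets or 2,940 reps per exercise, or equivalently 1,176 sets or 11,760 reps over the four exercises. These figures only multiply out what is already stated; no view is taken on the schedule itself.
- State that numerator and denominator are on the same scale in both arms.
- As a minor clarification, say on Appendix D and in the app specification whether sets are counted per exercise or summed over the four. For logs already collected, fix a reading rule or raise a query before the arms are compared.
- Separately, reconcile the one-month logging in section 8.1.3 with section 4 and the study calendar.

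The cost is a text correction in three places, one instruction line on the log and in the app specification, and one sentence in section 8.1.3. The sample size does not change.
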